In 2022 a meta-analysis performed by (**Grawish et al., 2022**)⁽²³⁾ indicated that DDM as a regenerative biomaterial has potential roles in tissue regeneration. However, in order to confirm these trials, further well-designed analyses are needed, and evaluation of adverse events in observational studies is also needed.

To our knowledge, DDM has not been investigated as scaffold in regenerative endodontics for permanent teeth.

Several studies were evaluate the regenerative effect of DDM at dentin-pulp complex through direct pulp capping technique, and it was found to possess the ability to activate the odontogenic differentiation of stem cells resident in the pulp tissues and induce reparative dentin formation. DDM also considered for alveolar ridge, maxillary sinus floor augmentations, socket preservation, furcation perforation repair, guided bone, and bioroot regenerations as well as bone and cartilage healing ⁽²³⁻²⁷⁾.

Hence, this study will be designed to evaluate regenerative effect of Demineralized Dentin Matrix as a scaffold in comparison to conventional blood clot in immature permanent teeth.

II. The null hypothesis

The null hypothesis is that there are no significance differences in the clinical and radiographic outcomes of regenerative endodontic of non-vital immature permanent teeth following the use of DDM in comparison to a blood clot scaffold.

III. Aim of the study

This study aims to:

Compare the clinical and radiographic outcomes of demineralized dentin matrix scaffold to blood clot scaffold in immature permanent incisors with non-vital pulps for one year.

IV. PICOTS

P: Patients ranging age 7–13years

I: Demineralized Dentin Matrix as a scaffold in Regenerative endodontic procedure

C: Blood clot scaffold Regenerative endodontic procedure

O: Clinical and radiographic success.

T: One year

S: outpatient's clinic of the Pediatric Dentistry and Dental Public Health Department, Faculty of Dentistry, Ain Shams University.

V. Methodology:

i. Study design

A Randomized, Controlled trial with 1:1 allocation ratio

ii. Sample size estimation

A power analysis was designed to have adequate power to apply a two-sided statistical test of the null hypothesis that there is no difference would be found between different groups. By adopting an alpha level of (0.05) a beta of (0.2) i.e. power=80% and an effect size (d) of

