(1.51) calculated based on the results of a previous study ⁽²⁵⁾. the predicted sample size (n) was a total of (24) cases (i.e. 12 cases per group). Sample size was increased by 20% to compensate for possible dropouts during follow-up intervals to be (30) cases (i.e. 10 cases per group). Sample size calculation was performed using G*Power version 3.1.9.7⁽²⁸⁾

iii. Assignment of intervention:

a. Randomization and Allocation concealment.

1- Type: block Randomization, with blocks numbers of 10 and 1:1:1 allocation ratio in to 3 groups

Group I: DDM (study)

Group II: (control) blood clot

Group III: (+ control) blood clot with collagen

2- Sequence generation: the most senior supervisor will generate the sequence of random numbers using online randomization (www.random.org).

Allocation concealment and implementation:

Allocation concealment will be ensured by preparing opaque envelopes containing one number from the generated random sequence for assigned group. The most senior supervisor will select an envelope and reveal the treatment group at the final regeneration visit.

b. Blinding:

double blind study, participants, outcome assessors, statistician will be blinded.

iv. Study setting

This study will be conducted at the Outpatients Clinic at the Department of Pediatric Dentistry and Dental Public Health, Faculty of Dentistry, Ain Shams University.

ii. Study methodology

ethical regulation:

The study protocol will be submitted to the Research ethics committee, Faculty of Dentistry, Ain Shams University for approval.

V. Population

All parent or legal guardian fulfill the eligible criteria will be signed an informed consent before beginning any procedure, explaining detailed treatment procedures, the possible outcomes, comprehensive discussions of the risks, complications, alternative treatment options, follow-up period needed, and sequel of no treatment⁽⁸⁻¹⁴⁾.

Inclusion criteria:

- (1) Age 7–13 years at the time of enrolment.
- (2) Provision of informed consent by one parent or legal guardian.
- (3) At least one immature permanent anterior tooth diagnosed with irreversible pulpitis or pulp necrosis with or without periapical lesions.
- (4) Restorable teeth.
- (5) Compliant patient/parent.
- (6) Patients not allergic to medicaments and antibiotics necessary to complete procedure (ASA 1 or 2).
- (7) Radiologic evidence of open apices (Teeth are considered immature when a minimum of 1 mm apical foramen width is evident)

Exclusion criteria

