- (1) Teeth with root fractures or split roots.
- (2) Presence of root resorptions.
- (3) Presence of periodontal pockets.
- (4) Developmental anomalies
- (5) Presence of periapical radiolucency more than 10 mm
- (6) Tooth with class III mobility.

vi. Clinical Procedures

a. Screening Recruitment

Patients attending the outpatient's clinic of the Pediatric Dentistry and Dental Public Health Department, Ain Shams University will be screened for eligibility. Only patients who met the inclusion criteria and sign the informed consent will be conveniently enrolled in the study until

the predetermined sample size is reached. All examination procedures will be done by the same operator to ensure standardization.

b. Informed Consent

A signed informed consent from parent or legal guardian, and an oral assent to the child, as outlined by the Research Ethics Committee, Faculty of Dentistry, Ain Shams University will be obtained before the conduction of the study.

Grouping:

Eligible immature anterior teeth will be randomly allocated in two groups:

Group I: 10 teeth will be treated with demineralized dentin matrix as scaffold in regenerative endodontic procedure.

Group II: 10 teeth will be treated with conventional regenerative endodontic procedure (blood clot scaffold).

Group III: 10 teeth will be treated with regenerative endodontic procedure (bloodclot and collagen scaffold).

Clinical procedures:

Pre-operative periapical radiograph and cone beam computed tomography CBCT will be taken on the selected non-vital tooth in each child before the beginning of the regenerative endodontic treatment procedure (29, 30).

RET will be carried out according to ASE⁽⁸⁾

First Appointment

- Local analgesia will be delivered (2% lidocaine with 1:100,000 adrenaline).
- Following rubber dam isolation and access cavity preparation, pulp tissue extirpation/debridement
- The root canal system will be minimally instrumented.
- Copious irrigation will be performed, gently with 20ml NaOCl (1.5% NaOCl (20mL/canal, 5 min) using 0.3mm gauge single side vented needles, adjusted 3 mm short of the apex.
- then canal will be irrigated with EDTA (20 mL/canal, 5 min), with irrigating needle that will be positioned about 1 mm shorter than the root end, to minimize cytotoxicity to stem cells in the apical tissues, followed by a final rinse 20 mL sterile saline .

- Canals will be dried with paper points.

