double antibiotic paste, ciprofloxacin (Ciprocin 250mg tablets) and Metronidazole (Flagyl 500mg tablets) in a 1:1 ratio will be mixed with sterile distilled water in a 3:1 ratio, then will be introduced into the root canal systems using 18 G hypodermic needle and will be packed gently down the root canal using a hand plunger, ensuring that there will be no remains coronal to CEJ

- A sterile dry cotton pellet will be placed over the paste after which the tooth will be sealed with 3-4mm of a temporary restorative material.
- Patient will be dismissed for 2 week

Second Appointment (two week after 1st visit)

- Response to initial treatment will be assessed. If there are signs/symptoms of persistent infection, additional treatment time with antimicrobial.
- Local Anesthesia without vasoconstrictor will be administered; dental dam isolation will be achieved.
- Copious gentle irrigation will be performed with 20ml of 17% EDTA, followed by a final rinse 20 mL sterile saline.
- Canals will be dried with paper points.

In group I: teeth will be treated with demineralized dentin matrix as scaffold in regenerative endodontic procedure

Teeth, in this group, will be anaesthetised using a local anaesthetic without vasoconstrictor. Demineralized dentin matrix will be introduced inside the root canal and bleeding will be created into root canal by over-instrumentation by rotating K-file at 2 mm past the apical foramen with the goal of having the entire canal filled with blood to the level of the cemento-enamel junction.

A lightly moistened sterile cotton pellet will be placed into the canal, 3-4 mm apical to the CEJ, for 7-10 minutes to allow blood clot formation.

Placement of the bioactive and restorative materials: A bioactive material such as tricalcium silicate will be placed over the blood clot as a capping material. A 3-4 mm layer of glass ionomer will be gently placed over the capping material.

Followed by resin composite restoration ⁽¹⁶⁾.

In group II: teeth will be treated with conventional regenerative endodontic procedure (blood clot scaffold).

Teeth, in this group, will be anaesthetised using a local anaesthetic without vasoconstrictor. Bleeding will be created into root canal by over-instrumentation

A lightly moistened sterile cotton pellet will be placed into the canal, 3-4 mm apical to the CEJ, for 7-10 minutes to allow blood clot formation.

Placement of the bioactive and restorative materials as mentioned above.

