In group III: teeth will be treated with conventional regenerative endodontic procedure (blood clot and collagen scaffold).

Teeth, in this group, will be anaesthetised using a local anaesthetic without vasoconstrictor. Bleeding will be created into root canal by over-instrumentation

A collagen will be placed into the canal, apical to the CEJ.

Placement of the bioactive and restorative materials as mentioned above

e. Follow up

Clinical and Radiographic examination will be carried out during follow up period^(15, 16).

1- Clinical evaluation: Treatment success will be assessed using following criteria of success.

Criteria of success: Absence of

- Pain
- Soft tissue swelling
- Soft tissue inflammation
- Sinus tract
- tenderness to percussion
- tooth mobility

2- Radiographic evaluation:

A-Conventional radiographic evaluation:

Criteria of success:

- Apical foramen width reduction
- Increased dentinal wall thickness
- Increased root length
- Conventional radiograph showing progress bone healing and presence of a normal periodontal ligament space.
- Reduction in size of the lesion.

B- CBCT evaluation:

- CBC with limited field of view will be carried out at 12 month to asses dentin width and length^(23, 28)

f. Outcome measurement

Outcome	assessment	Assessment method
Primary outcome	1- pain 2-pain percussion 3-pathological mobility 4- gingival becket	1-visual assessment 2-percussion test 3-blunt ends of two examination mirrors 4-graduated metal periodontal probe
Secondary out com	1-Root length 2-Root dentinal thickness 3- Apical foramen width 4- Total radiographic root area (absence of internal and external root resorption, widening of periodontal ligament space, new preabical radiolucencies or enlargement of pre-existing lesion, pulp canal calcification)	Digital periapical radiograph examination with using paralleling device
Secondary outcome	Increased root wall thickness and increased root length.	CBCT with limited field of view

VII. Statistical analysis

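### The primary outcome is four clinical signs that do not measure root development, and the stated 80% power, built on a difference in means, does not apply to them

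*Protocol*

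**What the plan says.** The last paragraph of the introduction states the purpose: "this study will be designed to evaluate regenerative effect of Demineralized Dentin Matrix as a scaffold in comparison to conventional blood clot". Section III (Aim) is wider: "Compare the clinical and radiographic outcomes of demineralized dentin matrix scaffold to blood clot scaffold in immature permanent incisors with non-vital pulps for one year". The null hypothesis and the PICOTS outcome also name both clinical and radiographic results.

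The table in section f (Outcome measurement) gives the primary outcome as "1- pain 2-pain percussion 3-pathological mobility 4- gingival becket". It labels the periapical measures (root length, dentinal thickness, apical foramen width, root area) and the CBCT measures (root wall thickness, root length) as secondary.

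Three other passages bear on how often the primary signs can occur:

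- The exclusion criteria include "Presence of periodontal pockets" and "Tooth with class III mobility".
- All arms share the same first appointment. At the second, "If there are signs/symptoms of persistent infection, additional treatment time with antimicrobial" is foreseen.
- Under allocation concealment, the senior supervisor is to "reveal the treatment group at the final regeneration visit", so the arms differ only from that visit.

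Section ii (Sample size estimation) uses two-sided alpha 0.05, 80% power and d = 1.51, and gives totals of 24 and, after dropout, 30 (10 per group). Section VII plans chi-square for categorical data, and a paired t-test or signed-rank test for numerical data.

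**The concern.** A primary outcome should answer the question the trial was set up to ask. Here the question is whether a scaffold regenerates tissue, and the primary outcome is whether a tooth is free of clinical signs. A tooth can be free of signs for a year with no root growth at all.

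The clinical signs may also separate the arms poorly. One of the four is absent at entry by criterion, and the shared disinfection phase treats the infection before the scaffolds differ. The sample size was calculated for another kind of variable, so the stated power gives no assurance for this one. A non-significant clinical comparison is then a likely result even if the scaffolds differ, and it could be reported as equal efficacy under a null hypothesis of no difference.

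**Working it through.** **1. Reproducing the plan's sample size.** Inputs from section ii: d = 1.51, two-sided alpha 0.05, power 80%. For a two-sample t-test (noncentral t), the required n per arm is 7.97, rounded up to 8, with power 80.2%. Three arms give 8 × 3 = 24. Allowing for 20% dropout, 24 / (1 − 0.20) = 30, or 10 per arm. The totals of 24 and 30 therefore reproduce for three arms. (The 12 per group in the same section does not; n = 12 would give 94% power. That is a separate matter.)

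The d in this calculation is a difference in means divided by a standard deviation, so it belongs to a continuous variable. The section does not name the variable. The source it cites (reference 25) is, by its title, about the effect of treated dentin matrix on differentiation of pulp stem cells.

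**2. What the same numbers give for a yes/no primary outcome.** Assumptions: the four signs are combined into success or failure per tooth (the table states no combining rule); 10 teeth per arm are evaluated; DDM is compared with blood clot by chi-square without continuity correction.

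For failures a and b among n = 10 per arm:

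χ² = 2n[a(n − b) − b(n − a)]² / [n · n · (a + b)(2n − a − b)]

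- 0 v 3 failures: 20 × 30² / (10 × 10 × 3 × 17) = 18000 / 5100 = 3.53, p = 0.060.
- 0 v 4 failures: 20 × 40² / (10 × 10 × 4 × 16) = 32000 / 6400 = 5.00, p = 0.025.

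So a DDM arm with no failures is significant only if at least 4 of 10 blood-clot teeth fail. Fisher's exact test would need 5 (0 v 4: p = 0.087; 0 v 5: p = 0.033).

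**3. Power under assumed success rates.** The protocol gives no event rates, so a range is shown. Power is the sum of the binomial probabilities of all tables with p ≤ 0.05. When DDM never fails, this is P(X ≥ 4) with X ~ Bin(10, blood-clot failure rate).

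| Success, DDM / blood clot (assumed) | Power, 10 per arm |
|---|---|
| 100% / 90% | 1.3% |
| 95% / 85% | 3.1% |
| 100% / 80% | 12% |
| 100% / 70% | 35% |
| 100% / 60% | 62% |
| 100% / 50% | 83% |

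In this range, 80% power is reached only when half of the blood-clot teeth fail and no DDM tooth does.

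**4. The same arms with a continuous primary outcome.** If d = 1.51 held for a CBCT measure (an assumption), 10 per arm would give 89% power for one pairwise two-sample comparison, and 8 per arm 80.2%.

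**The case against.** The strongest reply is that clinical outcome is a declared aim. The aim, null hypothesis and PICOTS all name it, and recurrent pain, tenderness or mobility over a year is a real failure that a new intracanal material could affect. This stands: a clinical primary outcome is not foreign to the trial, and which domain ranks first is partly a choice. It does not remove the mismatch with the stated regenerative purpose or with the power calculation.

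A reader might infer that entry criteria and disinfection remove all the primary signs before the scaffold is placed, so that nearly every tooth already meets the primary outcome. The documents do not support that. Only pockets are excluded outright. Mobility is excluded only at class III, pain and percussion tenderness are not exclusions, and teeth with irreversible pulpitis may enter. The second-appointment text extends treatment if infection persists; it neither requires signs to be gone nor drops any tooth, so the phase is not a selecting run-in.

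Nor would a null clinical result leave the trial with no information on regeneration, since the root measures remain planned secondary outcomes.

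The power figures also depend on assumed rates, and higher failure rates raise them. Low power at 10 per arm would affect any yes/no outcome. The threshold of 4 failures is pairwise: an overall three-arm chi-square with failures of 0, 3 and 0 gives χ² = 6.67 on 2 degrees of freedom, p = 0.036. Section VII does not say which comparison is meant.

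**Conclusion.** The point holds in this form. The primary outcome does not measure root development, although that is the purpose given for the study, and the 80% power does not apply to it. Both statements follow from the protocol alone.

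That events will be few is plausible from the pocket exclusion and the common disinfection, but it is not shown. The size rests on three assumptions: a single success/failure variable, a pairwise uncorrected chi-square test with 10 per arm, and success rates that the protocol does not give. If success is 80% or more in both arms, as in the first three rows of the table, power is about 1% to 12%. If blood-clot failures were as common as 40% to 50% against none with DDM, it would be 62% to 83%. A ceiling effect is therefore a risk and not an established fact.

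**What to change.** - **Section f:** make the change from pre-operative CBCT to 12 months in one named measure (for example root length) the primary outcome, for DDM against blood clot.
- **Section VII:** name a between-group test for it, for example ANCOVA on the 12-month value with the baseline value as covariate. The paired t-test and signed-rank test now listed for numerical data compare times within a tooth, not arms.
- **Section ii:** state that the power refers to that measure, after confirming that d = 1.51 applies to it. If it does not, redo the calculation.
- **Clinical signs:** keep them as a secondary outcome, reported as failure or relapse after scaffold placement, and state that a non-significant clinical comparison will not be read as equal efficacy.

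**Cost:** a protocol amendment with ethics review, and matching changes wherever the outcomes are registered. Both scans are already in the plan, so there are no added visits or scans, and no added patients unless the confirmed effect size is smaller. Clinical success would no longer be the headline result. Section VIII, which runs the whole study from October 2023 to October 2024, must be reconciled with enrolment, disinfection and a 12-month scan. The current plan already requires that scan, but the conflict matters more once it carries the primary outcome.

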Categorical data will be represented as frequency (n) and percentage (%) and will be analyzed using chi square test. Numerical data will be explored for normality by checking the data distribution, calculating the mean and median values and using Kolmogorov-Smirnov and Shapiro-Wilk tests. If the data was found to be normally distributed, it will be presented as mean and standard deviation values and paired t-test will be used for the analysis. If the assumption of normality was found to be violated; the data will be presented as median and range values and will be analyzed using Signed rank test. The significance level will be set at $p \leq 0.05$ for all tests. Statistical analysis will be performed with IBM SPSS Statistics Version 26 for Windows.

VIII. Study timeline

This study will be conducted from October 2023 to October 2024.

X. Patient withdrawal

- Patients who aren't willing to continue in the study will have the right to quit at any time without loss of any benefits.
- Patients who don't comply with the oral hygiene measures given will be excluded from the study and will be offered to continue dental treatment at the departments' outpatient clinic.
- Any adverse event will be recorded and managed promptly. In addition, in failure occurs, the use of the experimental material will be stopped and patients will be treated with another modality.

[figure not shown]
xi. Data management

Patient information will be guarded as confidential information that should never be revealed at all times.

All information will be kept as a hard and soft copy.

xii. Adverse event reporting

Regenerative treatment is not expected to have any adverse side effects on health but if failure occurs in the regenerative treatment, conventional regenerative endodontic treatment will be fabricated.

xiii. Ethics and dissemination

a. Research ethics approval:

This protocol and the template informed consent form contained in Appendix are written following the guidelines outlined by the Research Ethics Committee and Institutional Review Board, Faculty of Dentistry, Ain Shams University.

b. Protocol amendments:

In case of protocol modifications, the Research Ethics Committee and Institutional Review Board, Faculty of Dentistry, Ain Shams University will review and approve the changes of protocol before proceeding and implementation of changes.

c. Informed consent:

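### Chi-square is the only test named for categorical outcomes; with 10 teeth per arm falling to about 8, its true error rate can pass 5% after dropout, and an exact test should be named

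*Protocol*

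**What the plan says.** The protocol's section VII, Statistical analysis, gives one rule for categorical outcomes: "Categorical data will be represented as frequency (n) and percentage (%) and will be analyzed using chi square test". It adds "The significance level will be set at $p \leq 0.05$ for all tests". It names no exact test, continuity correction or condition on expected counts. For numerical data the same section does provide a fallback, a signed rank test if normality fails.

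Under Grouping, the first arm is "Group I: 10 teeth will be treated with demineralized dentin matrix as scaffold in regenerative endodontic procedure", and the other two arms have the same number. The sample size section reaches this by an increase "to compensate for possible dropouts during follow-up intervals to be (30) cases (i.e. 10 cases per group").

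The Outcome measurement table lists pain, percussion pain, pathological mobility and gingival pocket as primary. The clinical success criteria under Follow up score pain, percussion tenderness and mobility, among other signs, by their absence. They do not list the pocket.

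**The concern.** The Pearson chi-square p-value is a large-sample approximation. The usual guide is that every expected count should be at least 5, and with 8 to 10 teeth per arm this is hardly ever met. If the approximation is poor, the nominal 5% test may have a different true error rate, and a borderline difference between arms may be called significant by chi-square but not by an exact test. The clinical outcomes are primary, so such a result could decide the trial's main conclusion. If no alternative is fixed in advance, the choice between conflicting p-values would be made after the data are seen.

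**Working it through.** **Arm sizes.** The plan uses a "two-sided statistical test of the null hypothesis", alpha 0.05, power 80% and a standardised effect of 1.51. A two-sample t-test by the noncentral t distribution needs 8 per arm (power 0.802; 7 per arm gives 0.737). Then 3 × 8 = 24 and 24 / (1 − 0.20) = 30, so both printed totals reproduce as three arms of 8, raised to 10. Conversely, 10 × (1 − 0.20) = 8 per arm after the planned dropout. The protocol also prints "the predicted sample size (n) was a total of (24) cases (i.e. 12 cases per group"), which does not fit three arms; 12 per arm is checked below as well.

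**Expected counts.** With equal arms of n and overall event share s, the smallest expected count is n × min(s, 1 − s).
- n = 8: the maximum is 8 × 0.5 = 4, so 5 is never reached.
- n = 10: the maximum is 10 × 0.5 = 5, reached only with 10 events in 20 teeth, or 15 in 30.

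With two arms of 10, the chance of exactly 10 events is 0.2% at a 20% event rate, 3.1% at 30% and 17.6% at 50%. These rates are assumptions, because the protocol gives none.

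**True size.** For each pair of arm sizes, every 2×2 table was listed. Those with uncorrected Pearson p ≤ 0.05 were kept, and their binomial probabilities were summed at a common event rate.

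| Arms | Maximum true size | Lowest event rate at which size passes 5% |
|---|---|---|
| 10 v 10 | 4.2% | never |
| 10 v 9 | 6.5% | about 18% |
| 9 v 9 | 5.7% | about 26% |
| 10 v 8 | 5.3% | about 22% |
| 9 v 8 | 5.3% | about 23% |
| 8 v 8 | 7.7% | about 29% |
| 9 v 7 | 8.1% | about 20% |

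The picture is symmetric, so very common events behave like very rare ones. At 12 v 12 the maximum is 6.4%.

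The 8 v 8 maximum can be checked by hand. Pearson rejects exactly when the arms differ by 4 or more events. At a 50% event rate that probability is 2 × P(Bin(16, 0.5) ≥ 12) = 2 × (1820 + 560 + 120 + 16 + 1) / 65536 = 5034 / 65536 = 7.7%.

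At a 10% event rate the true size is 0.5% at 8 v 8 and 0.9% at 10 v 10. With three arms the maximum is 5.0% at 10 per arm and 6.0% at 8 per arm.

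**One table in full: 2/8 versus 6/8.** All four expected counts are 4.
- Pearson: 4 × (2²/4) = 4.0, p = 0.046.
- Fisher: 2 × (28×28 + 8×8 + 1×1) / 12870 = 1698 / 12870 = 0.132.
- Boschloo: 0.077.

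At 8 v 8, Pearson and Boschloo disagree at 0.05 on three patterns: 1 v 5 (0.039 against 0.053), 2 v 6, and 3 v 7 (the mirror image of 1 v 5).

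**At 10 v 10.** Pearson and Boschloo give the same decision on every table. For 0/10 versus 4/10, Pearson is 0.025, Boschloo 0.042 and Fisher 0.087. For 2/10 versus 7/10 they are 0.025, 0.041 and 0.070.

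**The case against.** The expected-count guide is a rule of thumb, and failing it does not by itself show a wrong error rate. A reader might infer from it that the chi-square test is invalid at the planned size. The figures do not support that: at 10 v 10 the true size never exceeds 4.2%. Where Pearson and Fisher disagree there, as for 0/10 versus 4/10, the gap reflects Fisher's conservatism (maximum size 1.3%), since Boschloo sides with Pearson. Likewise, three arms of 10 with 0, 0 and 3 events give Pearson 0.036 and Fisher-Freeman-Halton 0.089, yet the three-arm chi-square at that size has a maximum of 5.0%.

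The inflation is also a worst case. At 8 v 8 the size is 0.5% at a 10% event rate and 2.7% at 20%. If the signs are rare, the fault is conservatism.

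A reader might also take all four primary signs to be categorical. The protocol does not say so: pain has no stated scale, and the pocket is measured with a graduated probe, which can give a numerical reading. Nor is a table with no events a special harm of chi-square. The statistic is undefined there, but an exact test returns p = 1 and is no more informative.

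Finally, a small-count fallback might sit in a statistical analysis plan that is not shown. That narrows the point but does not remove it, because section VII fixes chi-square without exception.

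What stands is the behaviour after dropout, which the protocol itself plans for. The loss of one tooth (10 v 9) is enough to allow a size above 5%.

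**Conclusion.** The point holds in a limited form. Section VII commits at least percussion tenderness, mobility and clinical success to a large-sample test in arms of about 8 to 10 teeth. With no dropout, the two-arm test keeps its 5% level and an unconditional exact test would change no decision. With reduced arms, the true size can reach 6.5% to 8.1% for the least favourable splits examined (10 v 9, 8 v 8, 9 v 7) and 5.3% to 5.7% for the others. This happens only if the common event rate is moderate, from roughly 18% to 29% upward depending on the split. At low event rates the level is far below 5%. The conclusion rests on three assumptions: about 20% of teeth lost, event rates that the protocol does not give, and uncorrected Pearson as the meaning of chi-square. Whether pain and pocket are affected depends on how they are scored. The harm is modest, but the stated rule is easily corrected before data are seen.

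**What to change.** In section VII, replace the chi-square test with a prespecified exact test: Boschloo's (or Fisher's) for DDM versus blood clot, and Fisher-Freeman-Halton for three-arm tables. If Boschloo's is chosen, state how the two-sided p-value is formed, since definitions can differ in unequal arms, and confirm that the named software provides it.

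This takes about one sentence and changes no procedure, visit or sample size. The cost is that a few borderline results lose nominal significance. The loss is greater with Fisher, whose maximum size is 1.3% at 10 v 10 and 2.1% at 8 v 8; Fisher-Freeman-Halton reaches at most 4.1% with three arms of 10 and 2.5% with three arms of 8. Boschloo's test loses less, and at a full 10 v 10 it loses nothing against chi-square.

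### The protocol gives the measured radiographic outcomes only paired tests, so root length, dentinal thickness and apical width have no valid comparison between the independent arms

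*Protocol*

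**What the plan says.** Section VII (Statistical analysis) covers all numerical data with two tests. If the data are normal, "it will be presented as mean and standard deviation values and paired t-test will be used for the analysis". If they are not, the data "will be analyzed using Signed rank test". The only other test named is for categorical data: "Categorical data will be represented as frequency (n) and percentage (%) and will be analyzed using chi square test". No independent t-test, Mann-Whitney, ANOVA, Kruskal-Wallis or ANCOVA appears.

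The rest of the protocol describes a comparison of independent groups:

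- **Allocation.** The randomization section gives three groups in a 1:1:1 ratio. Under Grouping each group has its own teeth, for example "10 teeth will be treated with demineralized dentin matrix as scaffold in regenerative endodontic procedure". No split-mouth design or matching is described.
- **Hypothesis.** "The null hypothesis is that there are no significance differences in the clinical and radiographic outcomes", comparing DDM with a blood clot scaffold. The aim (section III) is the same comparison.
- **Sample size.** The power statement is for "a two-sided statistical test of the null hypothesis that there is no difference would be found between different groups".
- **Outcomes.** The outcome table lists root length, dentinal thickness and apical foramen width as secondary. The conventional radiographic criteria of success restate growth as yes/no items, such as "Increased dentinal wall thickness".

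**The concern.** A paired t-test or signed rank test needs two related values. In this design the natural pair is the pre-operative and the later measurement of the same tooth. The named tests therefore ask whether roots changed within an arm. Immature roots may grow under any scaffold, so a small p-value within the DDM arm says nothing about DDM relative to blood clot.

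Two things are at stake. First, with only within-arm p-values available, a result that is significant under DDM and not under blood clot invites reading as a scaffold effect, which is invalid. Second, the one between-arm test left, chi-square on yes/no growth, discards the amount of growth and has little power if most teeth in both arms show some increase.

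The protocol is not silent here. It fixes the wrong tests, and an analysis plan that followed it would inherit the error.

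**Working it through.** **1. Which test the stated sample size fits.** Inputs from the sample size section: d = 1.51, two-sided alpha 0.05, power 80%, 24 cases in total, 30 after a 20% allowance for dropout.

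For an independent two-sample t-test with n per arm, the noncentrality is d·√(n/2) on 2n − 2 degrees of freedom.

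| n per arm | Noncentrality | Power |
|---|---|---|
| 7 | 1.51 × √3.5 = 2.825 | 73.7% |
| 8 | 1.51 × √4 = 3.020 | 80.2% |
| 10 | 1.51 × √5 = 3.376 | 89.1% |
| 12 | 1.51 × √6 = 3.699 | 94.2% |

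So 8 per arm are needed, 3 × 8 = 24, and 24/(1 − 0.20) = 30. Both totals reproduce. The protocol's own breakdown of 24 into 12 per group does not fit three arms or 80% power.

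For a paired t-test with a standardised mean change of 1.51, the noncentrality is 1.51·√n on n − 1 degrees of freedom. Five pairs give 71.6% and six give 83.7%, so six would be enough. The stated total fits the independent test, not the paired one named in section VII.

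**2. Separate within-arm tests when the scaffolds do not differ.** The protocol gives no growth rate or SD. Assume the change is normal with SD 1 and mean μ in both arms, with μ from 0.5 to 1.5. Let p be the power of the paired t-test within one arm. Then P(DDM significant, blood clot not) = p(1 − p), and P(the arms disagree in either direction) = 2p(1 − p).

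| μ | p, n=8 | DDM only | Either way | p, n=10 | DDM only | Either way |
|---|---|---|---|---|---|---|
| 0.5 | 0.232 | 0.178 | 0.356 | 0.293 | 0.207 | 0.414 |
| 0.7 | 0.401 | 0.240 | 0.481 | 0.506 | 0.250 | 0.500 |
| 1.0 | 0.681 | 0.217 | 0.435 | 0.803 | 0.158 | 0.316 |
| 1.5 | 0.951 | 0.047 | 0.093 | 0.987 | 0.013 | 0.025 |

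The ranges are 1% to 25% and 3% to 50%. The upper ends are the mathematical maxima, reached at p = 0.5. A two-sample t-test on the change rejects in about 5%.

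**3. Chi-square on yes/no growth when the scaffolds do differ.** Assume control mean μ, DDM mean μ + 1.51, SD 1, and success defined as any increase. The success probabilities are Φ(μ) and Φ(μ + 1.51); at μ = 0.5 they are 0.691 and 0.978. Power is by exact enumeration of the Pearson test without correction.

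| μ | n=8 | n=10 |
|---|---|---|
| 0.5 | 18.5% | 30.8% |
| 0.7 | 9.5% | 18.2% |
| 1.0 | 2.5% | 5.6% |
| 1.5 | 0.1% | 0.3% |

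The independent t-test on the same data has 80.2% and 89.1%. If success is instead cut midway between the two arm means, the most favourable choice, chi-square reaches about 72% at either size.

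**The case against.** Nothing in the protocol supplies a between-arm test for the measured values, so the objections concern reach and size.

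- **The outcomes are secondary.** This is true. The primary items (pain, percussion pain, mobility, gingival pocket) read most naturally as present or absent and can go to chi-square. The pocket item, assessed with a graduated probe, would meet the same problem only if recorded in mm. The protocol does not fix its scale, and a yes/no reading is at least as natural. The case for correction rests on the radiographic outcomes being named in the hypothesis and the aim.
- **d = 1.51 is not tied to root growth.** This stands. The sample size section does not name the outcome or say that d applies to a change, and the cited source is, by its title, a study of stem-cell differentiation. The power contrast is a scenario.
- **Control growth might be close to zero.** This stands as a limit. At μ = 0 chi-square on any increase has 50% power (8 per arm) or 58% (10 per arm), still well below the t-test. The cut-off of any increase is also assumed, because the criteria give no threshold.
- **The t-test power is for one unadjusted pair.** Correct. With Bonferroni over three pairs it is 62.4% (8 per arm) and 76.1% (10 per arm).
- **The protocol never says it will compare p-values across arms.** Also true, but section VII offers no other test of the measured values.

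None of these makes a paired test suitable for independent arms.

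**Conclusion.** The concern holds. For numerical outcomes the protocol prescribes tests that cannot address its own null hypothesis, and this should be corrected before analysis. That conclusion needs no assumption: it follows from the tests named, the parallel allocation and the between-group hypothesis. It applies to the measured secondary radiographic outcomes and leaves the present/absent clinical items untouched.

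The size is illustrative. It assumes normal changes with equal SD, mean growth of 0.5 to 1.5 SD, and a true difference of 1.51 SD where power is quoted. On those terms a false one-sided pattern in favour of DDM arises in 1% to 25% of trials. A real difference of that size would usually be missed by chi-square on any increase (0.1% to 31% power) but usually found by an independent t-test (80.2% to 89.1%).

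**What to change.** In section VII, make a between-arm comparison of the 12-month measurements the main analysis of numerical outcomes. The preferred form is ANCOVA with arm as factor and the pre-operative value as covariate, reporting DDM minus blood clot with a 95% confidence interval. An independent t-test or ANOVA on the change would also cure the error. If the data are clearly non-normal, use Mann-Whitney (DDM against blood clot) or Kruskal-Wallis (three arms) on the change. Keep the paired tests as within-arm description only, and chi-square for the yes/no criteria.

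No new data are needed for the CBCT measures. At baseline, "Pre-operative periapical radiograph and cone beam computed tomography CBCT will be taken on the selected non-vital tooth in each child", and a 12-month CBCT is already scheduled. Apical foramen width is listed under periapical radiographs, for which the follow-up section gives no dates, so the 12-month film should be stated there. SPSS, the named software, runs all these tests. The cost is a change of wording, plus the ethics committee review that the protocol requires for any amendment.
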